5.4. Random Assignment Procedure

Participants will be assigned to one of two conditions (**XR-NTX-MMTx** or **XR-NTX+OTx**) using a random permutation procedure, such that, within gender for each block of 2, 4, or 6 participants, half will be assigned at random to the XR-NTX-MMTx Condition [$n=120$: 60 men, 60 women] and half to the XR-NTX+OTx condition [$n=120$: 60 men, 60 women], ensuring that both male and female participants have an equal chance of being assigned to either condition.⁸⁵ [Random block sizes will be used in order to conceal allocation to treatment condition. Sealed envelopes will be prepared for the study physician based on this block randomization procedure so that he can explain the condition to which a participant has been assigned. He will open the designated envelope and inform the participant to which one of the two conditions s/he has been assigned. This assignment procedure will be performed by the study physician so that, immediately after assignment to treatment condition, consent to medication initiation can be obtained from participants.

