2.7.3. A Phase 4, Pilot, Open-label Study of VIVITROL® in the Prevention of Re-arrest and Re-incarceration. This was a Phase 4B, open-label, longitudinal, single cohort, pre-post study. Pre-release opioid-dependent inmates from four Maryland area prisons (three for men and one for women) receive one injection of XR-NTX prior to release from prison and are then offered six monthly injections of XR-NTX for six months post-release. Following prison release, participants were seen for study visits and receive XR-NTX at Glenwood Life Counseling Center in Baltimore, MD. Participants were assessed at 10 time points: at screening (study entry: approximately one month prior to release from prison), at baseline (approximately 1 week prior to release), and then monthly for 6 treatment visits, an end-of-treatment visit, and a safety follow-up visit following their release from prison. We provided XR-NTX to 27 prisoners, of whom 100% received their first injection in prison; 21/27 (77.8%) received their first community injection, 18/27 (67%) received their second community injection; 13/27 (48%) received their third community injection; 11/27 (41%) received their 4th community injection, 10/27 (37%) received their 5th community injection, and 10/27 (37%) received their 6th community injection. Over the one-year enrollment period in this study, 97 individuals were screened for interest; 23 were initially not eligible, and 74 consented. Of these 74, 9 refused, 6 were released early and/or transferred to other prisons; 2 failed to meet the OUD criteria and 3 were positive for buprenorphine (all would have been ineligible for the presently proposed study). Fifteen inmates were excluded for medical reasons, 7 for psychiatric reasons and 5 for both psychiatric and medical reasons. According to the study physician and Co-I on the proposed study, [name], most, if not all, of these 27 excluded for medical and/or psychiatric reasons would have been eligible for the presently proposed study, as the proposed study would not exclude individuals with appropriately treated medical and/or psychiatric conditions. Results indicate participants completing 6 compared to participants completing less than 6 injections were less likely to test positive for opioids in the community (0% vs. 63%, respectively; $p=.003$). Although not statistically significant, individuals who did not complete all 6 injections were more likely to be re-arrested compared to those completing all 6 community injections (31% vs. 0%, respectively; $p=.12$).¹² The limitations of this study included a small sample size which was highly selective and lack of a comparator group. Finally, because the rather long list of exclusion criteria were mandated by the funding agency, the ability to generalize results is limited. The proposed study will have a larger sample size, comparator group, and less stringent exclusion criteria.

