5.2. Participant Eligibility: Inclusion/Exclusion Criteria

Eligible inmates must meet the following criteria: (1) adult male or female inmate at BCF, DRCF, BCCC, MCIW, CMCF, MCTC, or RCI and be eligible for release within 30 days; (2) history of opiate disorder [meeting DSM-V criteria of dependence at the time of incarceration; individuals who do not meet criteria at time of incarceration and become addicted during incarceration will be eligible]; Inmates not meeting the opioid-dependence criterion will be eligible if they were treated in an opioid agonist treatment program during the year before incarceration. (3) suitability for XR-NTX treatment as determined by medical evaluation; (4) currently opioid-free by history, with negative urine for all opioids and no signs of opiate withdrawal; (5) willingness to enroll in XR-NTX treatment in prison [not currently in or planning to pursue agonist (methadone, buprenorphine) treatment at release]; and (6) planning to live in Baltimore City or County (individuals outside of Baltimore City/county will be allowed to participate as long as they agree to travel to the treatment clinic if randomized to OTX). Inmates with one or more of the following conditions will be excluded from the study: (1) Liver function test levels greater than three times normal (note: if a blood specimen is unable to be drawn the individual will not be excluded from participation); (2) Active medical illness that may make participation hazardous (e.g., unstable diabetes, heart disease). Adequately treated medical conditions are acceptable; (3) Untreated psychiatric disorder that may make participation hazardous (e.g., untreated psychosis, bipolar disorder with mania). Adequately treated psychiatric disorders and appropriate psychotropic medications will be allowed; (4) History of allergic reaction to XR-NTX; (5) Current chronic pain diagnosis for which opioids are

prescribed; (6) creatinine above normal limits; (7) pregnancy (for women); (8) Breast-feeding (for women) (9) suicidal ideation (within the past 6-months); and (10) Body Mass Index (BMI) > 40.

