5.6. Medical Services in Prison

5.6.1. Treatment Clinic. Glenwood Life Counseling Center (GLCC) has been in continuous operation for 41 years. It is a State of Maryland- and CARF-certified outpatient drug treatment program that treats over 600 patients. GLC provides individual and group drug abuse counseling, HIV assessment and risk-reduction counseling, and a limited amount of family-based therapy. Its medical director, [name], served as the study physician on the PI's prison methadone, buprenorphine, and XR-NTX studies. The clinic is well-suited to continue its collaboration on the proposed study, in which it will provide XR-NTX services in the prison as well as in the community. [name] will perform all prison medical examinations and the nursing staff will provide prison-based injections under his supervision within 10 days of release.

5.6.2. Pre-release extended-release XR-NTX. XR-NTX treatment will likewise be administered by the nursing staff of GLCC under [name] supervision. Participants will receive one injection within 10 days prior to release. Long-acting, injectable naltrexone (Vivitrol®) will be used, at a dose of 4cc (380mg of

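### With printed block sizes of 2, 4 or 6, a physician who tallies past assignments could guess about 70% of the next ones (50% is chance) before judging eligibility

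*Combined protocol and SAP*

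**What the plan says.** Section 5.4 sets up permuted blocks stratified by gender: "within gender for each block of 2, 4, or 6 participants, half will be assigned at random". It gives the reason for varying the size: "Random block sizes will be used in order to conceal allocation to treatment condition". The device is an envelope: "Sealed envelopes will be prepared for the study physician based on this block randomization procedure". The physician learns each result: "He will open the designated envelope and inform the participant to which one of the two conditions s/he has been assigned".

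Section 5.3 places medical eligibility, and a discussion of the treatment with the study physician, before random assignment. Under 5.2 one criterion is "suitability for XR-NTX treatment as determined by medical evaluation"; others turn on whether an illness makes participation hazardous or is adequately treated. Section 5.6.1 says that the medical director of the treatment clinic "will perform all prison medical examinations". Section 2.7.3 refers to the "study physician and Co-I on the proposed study".

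The documents provided do not say who prepares or holds the envelopes, whether they are opaque and numbered, or whether eligibility is fixed in writing before one is opened.

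**The concern.** Varying the block size is meant to stop staff from working out the next assignment. It does so only in part when the blocks are very small, the sizes are known and every past assignment is known. A guesser need not know where a block ends. It is enough to know which arm is behind in that gender and to expect that arm next.

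Here the person who knows the past assignments seems to be the person who decides who is suitable, and he decides before the envelope is opened. Who is cleared, or when, could then follow the expected arm. Such selection happens before randomisation, so the intent-to-treat principle in 6.2 would not undo it, and adjustment for the three covariates in 6.4.1 would reach only what those covariates capture. Every outcome in Aim 1 would be exposed.

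**Working it through.** **Inputs from the protocol.** Block sizes 2, 4 and 6, half to each arm, within gender (5.4); 120 men and 120 women (1.1, 5.4); N=240.

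**Assumptions.** The mix of sizes is not stated, so I take the three as equally likely and show the range. The guesser knows the three possible sizes and all past assignments in that gender, but not the size of the current block. The plan gives no predictability figure to reproduce.

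**Step 1: guess rate.** The rule is to guess the arm that is behind and toss a coin when level (the Blackwell-Hodges convergence strategy). Expected correct guesses in a block of 2m are m + 2^(2m) / (2·C(2m, m)) − 1/2.

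| Block size | Correct guesses | Rate |
|---|---|---|
| 2 | 1 + 4/4 − 0.5 = 1.50 | 75.0% |
| 4 | 2 + 16/12 − 0.5 = 2.83 | 70.8% |
| 6 | 3 + 64/40 − 0.5 = 4.10 | 68.3% |

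Equally likely sizes: (1.50 + 2.83 + 4.10)/12 = 70.3%. Any mix lies between 68.3% and 75.0%. Simulating 120-person lists with the actual sizes hidden gives 70.2%, and a Bayesian guesser does no better than the simple rule.

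**Step 2: what the 70% consists of.** Correct guesses equal m plus half the number of assignments made when the arms are level. The expected number of level points is therefore 2 × (correct − m), that is 1.00, 1.67 and 2.20.

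- Coin flips: (1.00 + 1.67 + 2.20)/12 = 41%.
- Informed guesses: the other 59%. In the simulation each of these has a predictive probability of at least 75%.
- Share of informed guesses that are right: 6/12 ÷ 0.594 = 84%.
- Certain in advance: about 4% (simulation).

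**Step 3: what selection could do (illustration only).** Suppose the mean prognosis of those cleared is +δ SD when one arm is expected and −δ SD when the other is. With correct-guess rate p, bias = 2δ(2p − 1). The standard error of the difference is √(4/240) = 0.129 SD. Two-sided type I error is the chance that a normal variable with mean bias/0.129 falls outside ±1.96. The values of δ are assumed; nothing in the documents fixes them.

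| Scheme | p | δ (SD) | Bias (SD) | Type I error |
|---|---|---|---|---|
| 2/4/6 | .702 | 0.05 | 0.04 | .061 |
| 2/4/6 | .702 | 0.1 | 0.08 | .096 |
| 2/4/6 | .702 | 0.2 | 0.16 | .24 |
| 8/10/12 | .65 | 0.1 | 0.060 | .075 |
| Big-stick, limit 5 | .547 | 0.1 | 0.019 | .052 |

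**Step 4: the alternatives.** Under 8/10/12 the share predictable at 75% or better falls from 59% to about 20%, but 0.060/0.081, about three-quarters of the illustrated bias, remains. Under big-stick with limit 5, about 9% of assignments are forced and the rest are fair tosses: 0.09 + 0.91/2 ≈ 55%.

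**The case against.** The strongest reply is that the plan does conceal allocation: each assignment is in a sealed envelope and eligibility comes first. That stands. A reader might infer that small blocks leave allocation unconcealed, or that 70% of assignments are known beforehand. The documents support neither. The weakness is partial predictability; the gain over a coin is about 20 points, and only about 4% are certain. Nor should one rely on the 76% chance of the opposite arm after the first assignment of a block (1/3 × 1 + 1/3 × 2/3 + 1/3 × 3/5). It applies only when the guesser knows that a block has just begun, and varying sizes often hide that.

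Second, 70% is an upper bound. It needs separate tallies for men and women from month 6 to month 40 (7.0), and nothing says the physician would keep them. That stands, although five to six enrolments a month would make tallying easy.

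Third, there is little room for selection. Both arms get the same drug and the same prison injection, several criteria are measured (liver function, creatinine, BMI, pregnancy, urine), research staff make a preliminary determination, and release dates constrain timing. This narrows the discretion but does not remove it. In the pilot (2.7.3), 27 of 74 who consented were excluded on medical or psychiatric grounds, and the study physician considered that most, if not all, would be eligible here.

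Fourth, names are removed, so that the examiner, the envelope opener and the co-investigator are one person is a strong inference from 2.7.3, 5.4 and 5.6.1, not a stated fact. The investigators' section and the appendix forms are not available and may say more.

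Last, 4.1 can be read as blocking by facility as well as gender. With lists of about 20 the guess rate is 69.7%, so this changes little.

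**Conclusion.** The point holds as a structural weakness. Random sizes of 2, 4 or 6, printed in the protocol, protect less than 5.4 supposes: an observer who tracks assignments could guess about 70% of the next ones (68% to 75%), with 59% predictable at 75% or better. This rests on equally likely sizes, a tally by gender, and the envelope opener also being the examiner.

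A reader might go further and conclude that the comparison is biased. The documents do not support that: no selection is shown, and the bias and type I error figures follow from assumed shifts of ±0.05 to ±0.2 SD. The change is worth making because it is cheap and because selection of this kind cannot be repaired after enrolment.

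**What to change.** - **Preferred.** In 5.4, replace the 2/4/6 blocks by a big-stick rule within gender: a fair toss for each participant unless the arms differ by 5, when the next goes to the smaller arm.
- **Weaker alternative.** Drop the block of 2 and use larger random blocks such as 8, 10 and 12. This mainly reduces the highly predictable assignments.
- **With either.** Keep the limit or block sizes in the statistician's file and out of the protocol text held by the physician and research assistants. Record eligibility irrevocably before the envelope is opened. The record alone does not stop selection on an expected arm, but it prevents changes after opening and leaves a trail of exclusions. State who prepares and holds the envelopes and that they are opaque and numbered. Make 4.1 and 5.4 agree on whether facility is a stratum.
- **If staffing allows.** An eligibility assessor unaware of past assignments would bring the guess rate to 50% under any scheme.

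The cost is a new list and a short edit to 5.4. Arms may differ by about 5 to 6 within a gender. A difference of 5 in 120 leaves 1 − (5/120)² = 0.998 of the efficiency, a loss of about 0.2%.

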5.5. Participant Attrition

Consistent with our previous studies, we will collect detailed locator information that has enabled us in the past to successfully locate participants for follow-up. Thus, we anticipate follow-up rates well over 90%, which is consistent with our previous studies conducted at FRI.^{43,45-47,74,81}

5.6. Medical Services in Prison

5.6.1. Treatment Clinic. Glenwood Life Counseling Center (GLCC) has been in continuous operation for 41 years. It is a State of Maryland- and CARF-certified outpatient drug treatment program that treats over 600 patients. GLC provides individual and group drug abuse counseling, HIV assessment and risk-reduction counseling, and a limited amount of family-based therapy. Its medical director, [name], served as the study physician on the PI's prison methadone, buprenorphine, and XR-NTX studies. The clinic is well-suited to continue its collaboration on the proposed study, in which it will provide XR-NTX services in the prison as well as in the community. [name] will perform all prison medical examinations and the nursing staff will provide prison-based injections under his supervision within 10 days of release.

5.6.2. Pre-release extended-release XR-NTX. XR-NTX treatment will likewise be administered by the nursing staff of GLCC under [name] supervision. Participants will receive one injection within 10 days prior to release. Long-acting, injectable naltrexone (Vivitrol®) will be used, at a dose of 4cc (380mg of

naltrexone), administered by intramuscular injection to the buttocks (alternating sides monthly). Note: Participants can request to receive the intramuscular injection to the buttocks on the same side at each monthly visit. Vivivivrol® has the advantage of being FDA-approved for treatment of alcohol and opioid dependence, hence commercially available with strong safety data. Participants who deny opioid use in the past 10 days and who provide a specimen that tests negative for opioids on an instant urine test will receive a naloxone challenge test (Note: participants will receive two urine drug screens after consent: 1) one within 7-10 days of the injection; and 2) on the day of the injection). Naloxone is a short-acting opioid antagonist. This test consists of an intravenous (or intramuscular for participants' without venous access) injection of a 1.0mg of short-acting naloxone followed by a 20-minute observation period. A positive test will cause the temporary (up to 40 minutes) appearance of opioid withdrawal symptoms. Following a negative naloxone test, participants will be administered a low dose of oral naltrexone (12.5 mg) to further determine whether they will be able to tolerate depot naltrexone. If the participant has withdrawal symptoms in response to either the naloxone test or the oral naltrexone dose, the study physician will treat these symptoms with other medications. The medical staff of all prisons are highly experienced in treating opioid withdrawal, will be fully aware of the ongoing study, and will be able to provide symptomatic treatment to participants in the unlikely event that it is needed when study staff are not on the premises. Such issues may consist of the following: 1) withdrawal; and/or 2) injection site reaction. Prior to discharge, participants will receive an information card about naltrexone to carry with them at all times which will alert any medical providers about the characteristics of naltrexone. Ten days before anticipated release from prison, each participant will have an exit interview with the study's Research Assistant (RA). The RA will provide each such participant with a card with the address of GLCC outlining their schedule for their six monthly injections in the community. In addition, those randomized to XR-NTX+MMTx will receive a pamphlet 10 days before from the study RA detailing the procedures and operations of receiving medication at their place of residence. Follow-up injections will be scheduled 28 days (4 weeks) after first prison injection.

5.6.3. Overdose Prevention. The study physician and nurse will provide overdose prevention education at the time of XR-NTX injection in prison. We will use the overdose prevention video, "Staying Alive on the Outside" created by Green, Rich et al.⁸⁶ that was developed specifically for incarcerated populations and is currently used in Rhode Island Department of Corrections and other prison facilities. This video will be shown to all participants prior to release from prison. In addition, at each monthly follow-up visit in the community, the study nurse will provide prevention education information that was developed by the Substance Abuse and Mental Health Services Administration (SAMHSA). SAMHSA's Overdose Toolkit⁸⁷ is a guideline and checklist focusing on the following: 1) how to avoid overdose, 2) what is naloxone, 3) preventing overdose, and 4) reporting side effects. This checklist will be reviewed with all participants at their monthly visits with the study nurse.

5.7. XR-NTX Treatment in the Community

5.7.1. Glenwood Life Counseling Center for XR-NTX injections. The participants randomized to XR-NTX-OTx will go to GLCC only to receive injections under the direction of [name] and the study nurse from prison in order to ensure continuity of care for those receiving XR-NTX in the community (injections will occur every 28 days). The study RA will be in close contact upon release and will provide the client with reminder calls and/or visits prior to each XR-NTX appointment. Prior to each injection (at GLCC and place of residence), the nurse will administer: 1) a drug use questionnaire, and 2) an instant urine drug screening test. If negative for opioid use participants will be administered XR-NTX. If the participant reports using opioids in the past 7-10 days or tests positive on the urine drug screen they will not be administered XR-NTX (see procedures below for missed XR-NTX injections). Once the participant receives the injection, he/she will be monitored for up to 1½ hours. In addition, the nurse will provide the participant with the Naltrexone Medication Card, and tell the participant that he/she should keep it at all times. The nurse or physician will follow the same procedures as in prison.

5.7.2. Place of Residence for XR-NTX injections. For those randomized to receive XR-NTX at their place of residence, specific procedures will be implemented. First, the study nurse will be accompanied by the study RA so two staff members are always physically present. The study RA will confirm the place of residence prior to release from prison using our locator form. Contact will be made with the participant immediately following prison release and subsequently one week before each scheduled injection to verify his/her home address as

many newly released inmates have difficulty acquiring stable housing. The study nurse/RA will make sure the scheduled injection will be at a date/time that is convenient for the participant. In addition, the nurse/RA will reiterate to the participant that they will be asking sensitive questions and providing long-acting naltrexone so the participant may want to make sure they will have privacy. If the scheduled date/time is not convenient or the client feels as they will not have privacy the appointment will be rescheduled for a more convenient date/time. The nurse will be responsible for making sure the study team have all the necessary medical equipment. The nurse and RA will first knock on the door of the participant's residence and explain who they are and ask if the participant is there. If upon entering the residence, the nurse, RA or client feel that privacy is not possible they will reschedule another date/time that is convenient for both parties within 7 days. Moreover, if upon arriving the client is not present we will not disclose the reason for our appointment. The nurse/RA will leave a business card/appointment card to reschedule. At the place of residence, the nurse will administer XR-NTX and follow the same procedures as they would at the clinic (See above). Participants who enter a semi-controlled environment, such as residential or inpatient treatment, will still be eligible to receive XR-NTX if the program continues to allow them to receive it. We have fostered a relationship with many of the Baltimore City treatment programs and we will coordinate with them to continue to provide XR-NTX whenever possible. Individuals that are homeless or become homeless during the course of treatment will be offered the opportunity to receive XR-NTX at GLCC or FRI field office. Based on our previous prison studies with medication we anticipate no more than 4-6 participants will be homeless. Participants who are receiving XR-NTX at their place of residence who require additional medical care will be referred by the study nurse or physician based on their level of need, similar to as they would at a standard outpatient opioid treatment program. Participants will also be encouraged access to individual and group drug abuse counseling, HIV assessment and risk-reduction counseling, and family-based therapy on an as needed basis. *The study nurse will follow the Department of Health and Human Services, National Institute for Occupational Safety and Health Hazards Review manual (NIOSH)⁸⁸. This manual documents procedures and guidelines for providing medical care at a person's place of residence.*

5.7.3. Missed XR-NTX Injections. Participants who miss a monthly appointment will be contacted by the study RA within 24 hours of missing their appointment. The participant will be strongly encouraged to receive their next injection. If they miss a dose and return for a subsequent dose more than 7 days after their missed scheduled injection they will receive the following: 1) drug use questionnaire; 2) urine rapid test; and 3) naloxone challenge before the naltrexone injection. Everyone who reports opioid use or has a positive urine test for opioids during days 29-37 will be given the naloxone test and then the oral naltrexone (12.5mg) prior to the Vivitrol injection. If a participant misses a scheduled injection, he/she will have up to 37 days to receive their next XR-NTX injection. We will also record the number of successful rescues and number of delayed returns to XR-NTX treatment. Participants will no longer receive XR-NTX if they become incarcerated in jail or prison (if incarcerated less than 37 days, they will still be eligible receive their injection).

5.7.4. Withdrawal from Naltrexone: Treatment Safety. Participants may voluntarily stop taking XR-NTX doses at any time without penalty. Naltrexone is an opioid antagonist with no opioid agonist properties and no withdrawal upon discontinuation. Potential side effects relate to the medication itself and to the injection. The most frequent side effects of the medication include opioid withdrawal symptoms for those participants who still have some trace of opioids in their system. There had been reports of increased liver enzymes in individuals receiving high doses of oral NTX in a study of obesity. For this reason, we have an exclusion criterion regarding elevated liver function tests at baseline. The injection can lead to local irritation, infection, and potentially abscesses, which in the most extreme circumstance may require surgical debridement. Participants receiving XR-NTX who require acute treatment of pain will be told that they need to inform their physicians that they are on XR-NTX because XR-NTX is an antagonist and will block the effects of opioid-agonist pain medications. In addition, each participant will also receive a laminated card that indicates they are on XR-NTX that can be provided to their health care provider.

5.7.5. Additional Medical Concerns (Safety). Adverse events (AEs) and Serious Adverse Events (SAEs) will be tracked monthly at each follow-up appointment. In addition, in cases where participants have elevated liver enzymes and will be discontinued on XR-NTX, they will be linked with follow-up medical services to monitor liver function. All participants requiring additional medical or psychiatric care will be monitored and

followed up and be referred for additional care on a case-by-case basis. All participants are under the care of the study physician and GLC and will be monitored monthly through treatment phases. Where further medical treatment is required, appropriate referrals and consultation will be ongoing. Our study physician will follow the recommendations in the SAMHSA (2015) Clinical Use of Extended-Release Injectable Naltrexone in the Treatment of opioid Use Disorder: A Brief Guide by referring a patient for more intensive or specialized care.

